2.9. Case registration

(1) Case registration

Case enrollment should take place within 14 days prior to the start of radiotherapy (Day 1).

The attending doctors must obtain written consent based on the subject's own free will from those who meet the eligible criteria based on the inclusion/exclusion criteria. The attending doctors then prepare a case registration form that includes the subject identification number, the date of consent obtained, pre-registration assessment items, and the results of the confirmation of the inclusion and exclusion criteria.

A case registration form is prepared for each registered case and faxed to the research office. Research office: Department of Gastrointestinal Tract Surgery, Fukushima Medical University Hospital. [contact] (The case registration forms in Fukushima Medical University Hospital can use an alternative method to fax.)

The case registration form received by the research office is forwarded to the Data Center, which issues a receipt to the chief investigators at each institution, informing them of the registration number. The receipt form is sent to the principal investigator by fax.

In carrying out the above, the chief investigators at each institution prepare a list of subjects and maintain a list of subject identification numbers and registration numbers.

(2) Diagnostic imaging at registration

After case registration, the chief investigators send the imaging data to the research office as soon as possible. Before the start of radiotherapy, prior consultation is held with the Department of Radiation therapy, Fukushima Medical University Hospital regarding radiotherapy and diagnostic imaging at registration.

(3) Notification upon discontinuation of the study

If a subject enrolled in this study meets any of the following items, a discontinuation contact form is prepared and faxed to the research office.

Withdrawal of consent.

Termination of the study due to death.

Withdrawal from the study.

2.10. Statistical analysis

(1) Statistical analysis of the evaluation

The composition of the population to be analyzed shall be as follows:

- 1) All enrolled cases: the population of enrolled patients, excluding duplicate enrollments and incorrect enrollments.
- 2) All eligible cases: the population excluding ineligible cases (posterior ineligibility, ineligibility at enrollment, offending enrollment) from all enrolled cases.
- 3) Largest analyzed population (FAS): all eligible cases for whom treatment was administered.

(2) Method of analysis

Primary endpoints

- 1) Disease control rate

For FAS cases, summarize the responses of non-irradiated target lesions in a contingency table, and calculate the cumulative disease control rate and the Clopper & Pearson two-side 90% confidence interval. The disease control rate was defined as the total number of patients with CR/PR/SD divided by the number of eligible patients.

Secondary endpoint

- 1) MST

For FAS cases, estimate the MST using the Kaplan-Meier method, along with a two-sided 95% confidence interval using the Brookmeyer-Crowley method.

- 2) Safety

For all enrolled cases, data regarding AEs and toxicities were tabulated, and the Clopper & Pearson two-sided 95% CI was calculated.

- 3) Local control rate

For FAS cases, summarize the responses of irradiated target lesions in a contingency table, and calculate the cumulative disease control rate and the Clopper & Pearson two-side 90% confidence interval. The disease control rate was defined as the total number of patients with CR/PR/SD divided by the number of eligible patients.

- 4) Immunological parameters

Analyzes are performed at Fukushima Medical University Hospital, Kanagawa Cancer Centre,

and by outsourced testing, as appropriate.

2.11. During the study

Registration period: March 1, 2018 to August 31, 2020

Total study period: March 1, 2018 to August 31. 2021

3. Policy for selecting research subjects

3.1. Inclusion criteria

Subjects who meet all of the following criteria are eligible in this study.

- 1) Patients with unresectable advanced or recurrent gastric cancer with intolerance or progression after standard treatment (primary and secondary chemotherapy).
- 2) Patients with more than one measurable lesion and with at least one lesion ≥ 2 cm as defined by the RECIST guidelines edition 1.1 on diagnostic imaging (whole-body contrast-enhanced CT or PET-CT) within 14 days before entry.
- 3) Age ≥ 20 years.
- 4) ECOG performance status (PS): 0–2.
- 5) No contraindication for nivolumab (anti-PD-1 Ab) administration.
- 6) No contraindication for radiotherapy.
- 7) The patient's most recent laboratory tests within 14 days prior to enrollment must meet the following criteria. However, if the clinical examination at the time of enrollment is not included within 7 days prior to the first dose of nivolumab, a repeat examination should be performed within 7 days prior to the first dose of the study drug to reconfirm that the most recent clinical examination prior to the first dose of nivolumab meets the criteria below. In all cases, the laboratory values must not have received a G-CSF product or blood transfusion within 14 days prior to the date of testing.

White blood cell count $\geq 3,000/\mu\text{L}$ and neutrophil count $\geq 1,500/\mu\text{L}$

Hemoglobin $\geq 9.0 \text{ g/dL}$

Platelets $\geq 100,000/\mu\text{L}$

Total bilirubin ≤ 2.0 times the institutional standard upper limit (ISUL)

AST (GOT) and ALT (GPT) ≤ 3.0 times ISUL (in case with liver metastasis, ≤ 5.0 times ISUL).

Serum creatinine ≤ 1.5 times ISUL or creatinine clearance (Ccr) estimate $\geq 60 \text{ mL/min}$.

Ccr is calculated by the Cockcroft-Gault formula:

Male Ccr = $\{(140 - \text{age}) \times \text{weight (kg)}\} / \{72 \times \text{serum creatinine level (mg/dL)}\}$

Female Ccr = $0.85 \times \{(140 - \text{age}) \times \text{weight (kg)}\} / \{72 \times \text{serum creatinine level (mg/dL)}\}$

- 8) Patients expected survival ≥ 3 months.

9) Written informed consent is obtained from the patient prior to study enrollment.

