If the above criteria are not met, irradiation is postponed on a day-to-day basis until the criteria are met.

Nivolumab (anti-PD-1 Ab) treatment

Dosage and administration

In accordance with the recommended treatment for unresectable advanced or recurrent gastric cancer, 3 mg/kg (body weight) of nivolumab once every two weeks over at least one hour, or 240 mg once every two weeks over at least 30 minutes, is administered via intravenous infusion.

A total of six administered doses is considered the completion of protocol treatment, but there are no specific provisions for treatment after completion.

Continuation of treatment with nivolumab is also permitted within the insurance coverage at the discretion of the attending doctor.

However, any 'unacceptable concomitant or supportive therapy' as defined in 2.4.3) shall be considered a protocol deviation.

Dosing conditions

All of the following conditions should be met when starting administration of this drug.

- 1) White blood cell count \geq 3,000/ μ L and neutrophil count \geq 1,500/ μ L
- 2) Hemoglobin \geq 9.0 g/dL
- 3) Platelets \geq 100,000/ μ L
- 4) Total bilirubin \leq 2.0 times the upper limit of the institutional reference value
- 5) AST (GOT) and ALT (GPT) \leq 3.0 times the upper limit of the facility reference value. (If liver metastases are present, \leq 5.0 times the upper limit of the institutional reference value.)
- 6) Serum creatinine \leq 1.5 times the upper limit of the facility reference value or creatinine - clearance(Ccr) estimate \geq 60 mL/min.

Basis for setting

It is expected that radiotherapy will enhance the efficacy of anti-tumor immunity. We speculate that the use of nivolumab in combination with post-irradiation therapy may induce an abscopal effect in some cases. We decided to start nivolumab between Days 15-22, with Day 1 as the start date of radiotherapy. Because IFN- γ and TNF- α in serum increased about 10-14 days after irradiation (mouse model) (4), and immune responses such as CTL activation were observed about 2 weeks after administration of peptide vaccines and activated dendritic cells (clinical observation).

A possible disadvantage of this treatment strategy is that the combination of radiotherapy and nivolumab may increase or intensify adverse events; however, as far as we have searched, there have been no reports of serious adverse events occurring.

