During the course of nivolumab treatment, if palliative radiotherapy becomes necessary due to symptoms such as pain and bleeding worsen caused by an increase in lesions other than those treated with radiotherapy, radiotherapy should be allowed and observation continued if there are other evaluable lesions with no history of radiotherapy.

2) Unacceptable concomitant and supportive therapies

During protocol treatment (from the start of radiotherapy until after the sixth dose of nivolumab), none of the following treatments should be administered. Any of the following treatments are considered a protocol deviation.

- ① Treatment for cancers other than this protocol (chemotherapy, surgery, radiotherapy, endocrine therapy, immunotherapy, etc.). However, radiotherapy is permitted if the provisions of 2.4.1.⑤ are met.
- ② Other treatments presumed to influence the assessment of efficacy and safety in the study.
- ③ Immunosuppressive therapy. However, corticosteroids are only allowed in doses of hydrocortisone \leq 200 mg/day for transfusion allergy and small-dose steroids (< 15 mg/day of prednisone) for the prevention of cerebral hypertension symptoms and adrenal insufficiency.
- ④ Administration of other study medicines, including development products.

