2.5. Criteria for changes in dosage/use

1) Radiation dose escalation and dose reductions will not be performed. Nivolumab dosage and administration should be in accordance with the recommendations for the treatment of unresectable advanced or recurrent gastric cancer (Appendix).

2) Criteria for discontinuation of treatment

- ① Nivolumab (anti-PD-1 Ab) discontinuation criteria:
 - 1) Failure to meet the criteria for initiation of nivolumab (anti-PD-1 Ab) in '2.3.(2) Nivolumab (anti-PD-1 Ab) treatment' and failure to resume treatment within 14 days of the planned treatment date.
 - 2) If a patient requests discontinuation of nivolumab treatment, irrespective of whether or not it is associated with an adverse event.
 - 3) Death during protocol treatment.
 - 4) Ineligibility due to a known protocol violation, change of pathology diagnosis after enrolment, etc.
 - 5) It is deemed inappropriate to continue treatment due to apparent worsening of clinical symptoms caused by disease progression.
 - 6) Occurrence of Grade 2 or higher interstitial lung disease.
 - 7) Occurrence of Grade 2 or higher eye disorders.
 - 8) Occurrence of Grade 3 or higher bronchospasm, diarrhea, colitis, neurotoxicity, hypersensitivity reactions and injection reactions.
 - 9) Occurrence of Grade 3 or higher thrombocytopenia.
 - 10) Abnormalities in liver function that fulfill one of the following criteria have emerged. AST or ALT $> 5-10$ times the upper limit of the facility reference value for more than 2 weeks.

AST or ALT > 10 times the upper limit of the facility reference value. Total bilirubin levels > 5 times the upper limit of the institutional reference value. Concurrent AST or ALT > 3 times the upper limit of the facility reference value and total bilirubin > 2 times the upper limit of the facility reference value.

11) The principal investigator or a member of research team decides that continued treatment with nivolumab is not appropriate.

② Criteria for discontinuation of radiotherapy

Discontinue radiotherapy if any of the following occur:

- 1) Failure to meet the treatment criteria for radiotherapy in '2.3(2) – Radiotherapy'.
- 2) When the attending doctor decides that discontinuation is necessary due to an adverse event.
- 3) If the patient requests discontinuation of radiotherapy, irrespective of whether or not it is associated with an adverse event.
- 4) Patient deaths.

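### Inclusion criterion 7 allows a transfusion or G-CSF given after Day 1 to make an irradiated, nivolumab-dosed patient ineligible and removable from the FAS

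*Protocol*

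**What the plan says.** **Eligibility.** Protocol 3.1 makes a subject eligible only if every listed criterion is met. Criterion 7 sets laboratory limits at enrolment. Where the enrolment test is not within 7 days of the first nivolumab dose, it asks for a repeat test "to reconfirm that the most recent clinical examination prior to the first dose of nivolumab meets the criteria below". It adds that, in all cases, "the laboratory values must not have received a G-CSF product or blood transfusion within 14 days prior to the date of testing".

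**Dosing.** Protocol 2.3 repeats the same laboratory limits: "All of the following conditions should be met when starting administration of this drug". It says nothing about transfusion or G-CSF. Among nivolumab discontinuation criteria, 2.5 lists failing these conditions with "failure to resume treatment within 14 days of the planned treatment date" (criterion 1) and, separately, "Ineligibility due to a known protocol violation, change of pathology diagnosis after enrolment, etc" (criterion 4).

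**Analysis sets.** Protocol 2.10 and SAP 3.1 define all eligible cases as "the population excluding ineligible cases (posterior ineligibility, ineligibility at enrollment, offending enrollment) from all enrolled cases", and the FAS as the eligible cases who were treated. For the primary endpoint, 2.10 adds: "The disease control rate was defined as the total number of patients with CR/PR/SD divided by the number of eligible patients". Under SAP 3.1 the principal investigator settles case handling before data fixation, after a case review meeting. SAP 6.5 plans no sensitivity analysis.

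**The concern.** An analysis set for a single-arm trial should be fixed by facts that predate treatment. Here one eligibility item is measured after irradiation has started, and the analysis-set definitions remove posterior ineligibility as a category distinct from ineligibility at enrolment. The primary set and its denominator can then depend on how a patient fared after Day 1, and the decision is taken in an open-label trial.

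The exposed patient is one who received a transfusion or G-CSF in the 14 days before the re-test and then met the limits. Section 2.3 allows dosing and 3.1 says ineligible. Neither document says which rule prevails.

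**Working it through.** **1. When the re-test falls.** Enrolment precedes Day 1 (2.9), and nivolumab starts between Days 15 and 22 (2.1, 2.3). An enrolment test is therefore never within 7 days of the first dose, and the re-test is always due. Earliest day: 15 − 7 = Day 8; for a Day 22 start, 22 − 7 = Day 15.

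**2. What the bar covers.** For a Day 15 dose the latest possible test is on Day 15, which looks back to Day 1 (15 − 14 = 1); earlier tests look back further. Any transfusion or G-CSF from Day 1 up to the test breaks criterion 7. Section 2.4 contemplates transfusion during protocol treatment, since it allows hydrocortisone up to "200 mg/day for transfusion allergy and small-dose steroids", but no frequency is given.

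**3. The rules side by side.**

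| Irradiated patient | 2.3 / 2.5 | 3.1 criterion 7 |
|---|---|---|
| Delayed, then passes without support | Dosed | Eligible (the most recent test counts) |
| Passes after transfusion or G-CSF within 14 days | Dosed, may receive all six doses | Not met: ineligible |
| Never passes, never dosed | Discontinuation (criterion 1) | Unclear: the clause refers to a first dose that does not occur |

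The direct conflict is in the second row.

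**4. The plan's own figure.** Section 2.8 gives 39 patients for 40% against 60%, one-sided 5%, power 80%. The arcsine formula reproduces it: [(1.645 + 0.842) / (2 arcsin √0.6 − 2 arcsin √0.4)]² = 38.1, rounded up to 39. Planned enrolment is 40.

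**5. Success rule (assumed).** Neither document states one. I take success to be a lower two-sided 90% Clopper-Pearson limit above 40%, as the one-sided 5% design implies. The lower limit is the 0.05 quantile of Beta(x, n − x + 1).

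**6. Effect of k removals from 40.** The true rate over all 40 is 40%, or 16 expected controlled. If the removed patients have disease control rate q, the rate among those left is p = (16 − kq)/(40 − k). The one-sided error is P(X ≥ critical count) for X binomial(40 − k, p).

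| k | n | Critical count | Unrelated (q = 0.40) | All uncontrolled (q = 0) | Mostly controlled (q = 0.60) |
|---|---|---|---|---|---|
| 0 | 40 | 22 | 0.039 | 0.039 | 0.039 |
| 1 | 39 | 22 | 0.028 | 0.038 | 0.024 |
| 2 | 38 | 21 | 0.041 | 0.070 | 0.030 |
| 3 | 37 | 21 | 0.029 | 0.068 | 0.018 |
| 4 | 36 | 20 | 0.043 | 0.120 | 0.023 |

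The error passes 0.05 only if q is below 0.258 (k = 2), 0.155 (k = 3) or 0.345 (k = 4), and never for k = 1. The unevenness across k comes from the whole-number critical counts. If removals are instead random, with an expected share of 5% or 10% and all uncontrolled, the error is 0.061 or 0.105.

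**7. A borderline result can move either way.** 21/40 has lower limit 38.5% and fails; dropping two uncontrolled patients gives 21/38, lower limit 40.7%, which passes. 22/40 has lower limit 40.9% and passes; dropping one controlled patient gives 21/39, lower limit 39.6%, which fails.

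**8. Keeping everyone.** If the k patients stay in as not controlled, the error is P(X ≥ 22) for X binomial(40 − k, 16/(40 − k)): 0.038, 0.036, 0.035 and 0.033 for k = 1 to 4.

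**The case against.** The best defence is that the plan never intends a failed on-treatment test to undo eligibility. Section 2.9 has the criteria confirmed on the registration form, before Day 1. The protocol's one concrete example of ineligibility arising later is a changed pathology diagnosis, which is a baseline fact found late. For the patient who never passes, the re-test clause has no first dose to refer to, 2.5 criterion 1 names the event as a treatment discontinuation apart from ineligibility, SAP 5.2 tabulates incomplete treatment within the FAS, and SAP 6.7 analyses survival by treatment completion. Removals would also be visible: SAP 4 counts each population and SAP 8.2 lists FAS exclusions with reasons.

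Most of this stands for the never-dosed patient, who more naturally remains in the FAS, although no sentence says so. It does not settle the dosed patient. There the first dose occurs, the re-test is due, and 3.1 applies its bar in all cases. Listing an exclusion shows it without preventing it. The defence is also right that the evidence for transfusion is thin, a steroid allowance only, and that a dosed patient may well be controlled.

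**Conclusion.** The conflict between 3.1 and 2.3 is real and should be resolved. As written, an irradiated and dosed patient can be taken out of the primary analysis set and the denominator because of support given after treatment began.

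The size is uncertain. The number affected is unknown, and 1 to 4 of 40 is an illustration. With removals unrelated to outcome the one-sided error is 0.028 to 0.043, so there is no inflation. For dosed patients the direction is not fixed. All error figures rest on the inferred success rule.

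A reader might infer that everyone who fails the re-test is dropped, which inflates the error to 0.070 or 0.120. The documents do not support that. Those values need every removed patient to be uncontrolled. That fits chiefly the never-dosed patient, who cannot meet the 2.6 definition of SD without a sixth dose, and that is the patient whom 2.5 and the SAP point towards keeping. Nor is the adverse-event analysis exposed: 2.10 uses all enrolled cases and the SAP all treated enrolled cases.

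**What to change.** - **3.1, criterion 7:** delete the re-test sentence and limit the transfusion/G-CSF bar to the enrolment test.
- **2.3:** require the laboratory test for the first dose within 7 days before it. Do not add the bar as a dosing condition: a patient transfused on Day 14 could not be tested until about Day 28 (14 + 14), past the Day 15 to 22 start window.
- **2.10 and SAP 3.1:** state that FAS eligibility is judged only on the patient's status before Day 1, even if discovered later. Referring to status, not to the date of the data, still allows removal of a baseline misdiagnosis found afterwards.
- **2.10 and SAP 3.1:** state that an irradiated patient who fails, or is delayed by, the dosing conditions stays in the FAS and the denominator, counted as not controlled unless CR, PR or SD is documented. This must take precedence over the 2.6 sentence that leaves unevaluable lesions out of the analysis.

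The cost is a few sentences, with no extra patients, visits or data. The observed disease control rate may be slightly lower: for example, 16/40 is 40.0%, where 16/38 would have been 42.1%.

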3.2. Exclusion criteria

Subjects who meet the following criteria are not eligible to enroll in this study:

- 1) Patients with no tumor lesions that can be irradiated.
- 2) Patients with metachronous and simultaneous overlapping cancers (excluding intraepithelial cancer of the uterine cervix, fully treated basal cell carcinoma of the skin, and malignant tumors that were treated more than 5 years ago and have not recurred).
- 3) Patients with a history of severe hypersensitivity reactions to other Ab products.
- 4) Patients taking immunosuppressive drugs or corticosteroids (prednisone or prednisolone equivalent ≥ 15 mg/day).
- 5) Patients with active autoimmune diseases or a history of recurrent autoimmune diseases (patients with type-1 diabetes, hypothyroid controllable by hormone replacement therapy, and dermatosis without the need for systemic therapy are eligible).
- 6) Patients with complications or history of interstitial pneumonia or pulmonary fibrosis diagnosed by imaging studies or clinical findings.
- 7) Patients with presence of severe disease or medical condition such as severe nutritional deficiencies, transient ischemic attack within 180 days prior to enrollment, cerebral vascular attack within 180 days prior to enrollment, thrombus or thromboembolism within 180 days prior to enrollment, congestive heart failure (NYHA class III or IV), unstable angina, myocardial infarction within 12 months, severe arrhythmias requiring medication, conduction abnormalities such as AV block beyond the second degree, uncontrollable hypertension, liver cirrhosis (Child Class B or higher), mental disorders that may interfere with compliance with this study protocol, unstable diabetes, uncontrolled pericardial fluid, uncontrolled ascites, uncontrolled pleural effusions, diseases requiring anticoagulation therapy (excluding antiplatelet therapy including low-dose aspirin), and systemic infection with treatment.
- 8) Pregnant or lactating female.
- 9) Fertile female who are unwilling to use contraception.
- 10) Fertile male who are not willing to use contraception during study drug administration and for 7 months after study completion (if the partners are fertile females).
- 11) Prohibited previous treatment
Within 56 days of registration: radioactive drugs (except radiopharmaceuticals for examination or diagnostic purposes).
Within 28 days of registration: corticosteroids (excluding temporary use and prednisone or prednisolone equivalent ≤ 15 mg/day), immunosuppressant drugs, anti-cancer drugs, adhesive

treatment of pleura or pericardium, surgery with general anesthesia, and unapproved drugs.

Within 14 days of registration: surgery with local or superficial anesthesia.

12) Participating in other clinical trials or clinical studies (excludes those without intervention).

13) Patients with a positive HIV antigen/Ab test or HTLV-1 Ab test.

14) Patients who have history of treatment using ONO-4538, anti-PD-1 Ab, anti-PD-L1 Ab, anti-PD-L2 Ab, anti-CD137 Ab, anti-CTLA-4 Ab, or other Ab or drug therapies for T-cell regulation.

15) Patients determined by the investigator to be ineligible for participation in this study.

4. The scientific rationale for the research

This clinical trial is designed to investigate the additive effect of nivolumab and radiotherapy in patients with unresectable advanced or recurrent gastric cancer with intolerance or progression after standard treatment (primary and secondary chemotherapy), by administering the insured radiotherapy immediately before nivolumab treatment, a third-line treatment indicated by insurance. The results of basic and preclinical studies, as well as those of case reports, suggest that the combination of radiotherapy and anti-cancer immunotherapy may have a synergistic anti-tumor effect. However, no clinical trials similar to this study have been reported to date in patients with gastric cancer, and this study is a phase I/II clinical study exploring safety, clinical efficacy, and immunological changes of the combination therapy using radiotherapy and nivolumab in patients with unresectable advanced or recurrent gastric cancer. The number of planned cases is considered to be the minimum required for statistical purposes.

5. The procedure for obtaining informed consent

